2.4 Rationale

PD-1 directed therapy has demonstrated activity in squamous cell carcinomas of the head and neck (SCCHN), with response rates of 14-18% and a 31-32% disease control rate in studies testing PD-1 and PD-L1 inhibitors [25, 51]. However, the majority of head and neck patients treated with PD-1 directed therapy will likely experience disease progression. Although mechanisms of primary and secondary resistance to PD-1 therapy in head and neck cancer remain undefined, studies in non-small cell lung cancer patients and melanoma patients treated with PD-1 therapy suggest that resistance may be mediated in part by: 1) Failure to recognize tumor antigens and generate an initial immune response [52]; and/or 2) Limited access of effector T-cells to the tumor microenvironment to mediate an anti-tumor immune response potentiated by PD-1 blockade [53]. There is also evidence that large volume / bulky metastatic disease may be more immune suppressive and may respond less well to immune checkpoint blockade therapy. [54, 55]

Radiation therapy has known immunologic activity, and has demonstrated synergy with PD-1 blockade in multiple preclinical models [44, 56]. Specifically, radiation may overcome two hypothesized mechanisms of resistance to PD-1 therapy. Preclinical studies and translational investigations in human patients have demonstrated that radiation may lead to increased antigen recognition and epitope spreading [44, 57]. Preclinical and human studies have also demonstrated that radiation may impact the tumor microenvironment, leading to increased infiltration of effector T-cells, and decreased levels of inhibitory regulatory T-cells and myeloid derived suppressor cells [58]. In certain circumstances, these effects may lead to responses in patients who had previously progressed on checkpoint blockade, as has been demonstrated in case reports [57] and retrospective studies [59], including our experience that found improved systemic response following palliative radiotherapy in melanoma patients treated with ipilimumab [60]. Multiple

CONFIDENTIAL

This document is confidential. Do not disclose or use except as authorized.

radiation fractions / courses could potentially overcome resistance to PD-1 directed therapy and prime a systemic response in certain patients compared to a single fraction of radiation.

Preclinical studies demonstrate that fractionated high dose radiation may be optimal to promote targeted immunologic death of irradiated tumor cells leading to recognition of tumor antigens and a systemic anti-tumor immune response [40]. However, this single irradiated lesion may or may not lead to T-cell infiltration of remote, unirradiated lesions, and it is generally not feasible to irradiate multiple lesions to high doses because of toxicity concerns. In contrast, low dose radiation may be best suited to lead to T-cell infiltration and preferential expansion of effector as opposed to inhibitory T-cells within the tumor microenvironment [49]. Mathematical modeling also suggests that the site of the lesion irradiated to high dose may affect T-cell trafficking of activated T-cells to unirradiated lesions [61].

This study is informed by the preclinical and clinical data referenced above. In order to explore mechanisms of resistance to PD-1 blockade and optimize the use of targeted radiation to overcome this resistance, this phase 2 study will enroll SCCHN patients who have progressed on or shortly after prior PD-1 directed therapy. Restaging will be performed after initial course of radiation and pembrolizumab, and pembrolizumab will continue in patients that demonstrate a sustained response.

2.5 Correlative Studies Background

There is great utility to identifying mechanisms of resistance to PD-1 blockade as well as the mechanisms by which radiation may overcome this resistance. Based on prior studies conducted in patients across several disease types, expression of PD-L1 on tumor cells and tumor infiltrating immune cells could potentially serve as a predictor of response, at least in patients treated with PD-1 therapy alone. Tumor infiltrating lymphocytes at baseline may also serve as a predictive marker in patients treated with PD-1 blockade, although this has not yet been demonstrated in head and neck cancer. Additionally, it is unknown if these mechanisms of resistance may be impacted by focal radiation therapy, either delivered to a high or low total dose.

By performing biopsies on patients with disease resistant to PD-1 inhibition, and analyzing the tumor tissue for PD-L1 expression and infiltrating lymphocytes, we will investigate these potential mechanisms of resistance to PD-1 checkpoint blockade. Additionally, serial biopsies and blood collection obtained when feasible will evaluate the impact of radiation on these parameters and association with subsequent response.

In addition to radiation dose, the location of the irradiated lesions may also impact the ability of targeted radiation to stimulate an abscopal response [61] due to the likelihood of T-cells trafficking from the irradiated lesions to distant sites of disease. Algorithms incorporating T-cell homing may potentially be able to provide rational basis to target lesions most likely to generate an abscopal response.

3. PARTICIPANT SELECTION

3.1 Eligibility Criteria

CONFIDENTIAL

This document is confidential. Do not disclose or use except as authorized.

Participants must meet the following criteria on screening examination to be eligible to participate in the study:

1. Pathologically confirmed squamous cell carcinoma of the head and neck with evidence of metastatic disease or locally recurrent disease. Patients without pathologic or cytologic evidence of metastatic disease should have unequivocal evidence of metastasis from physical examination or radiologic evaluation.
2. Patients must have evidence of radiologic or clinical disease progression during or within 6 months of previous treatment with systemic PD-1 directed therapy, or have stable disease on prior PD-1 therapy (at least 6 doses) and/or have been deemed not to derive clinical benefit from PD-1 directed treatment. PD-1 directed treatment includes treatment with antibodies targeting the PD-1 receptor such as pembrolizumab or nivolumab, as well as PD-L1 targeted antibodies such as durvalumab. These agents may have been administered as part of a clinical trial, and/or in combination with other immunologic agents such as CTLA-4 inhibitors or other investigational or standard of care agents/treatments.
3. Patients must have least 1 non-CNS based lesions. Palliative radiation must be potentially indicated for at least one lesion, and this lesion must be a reasonable candidate for radiation to a dose of 8 Gy in each of 3-5 fractions as deemed by a treating radiation oncologist in terms of the ability to meet standardly accepted radiation dose constraints. Any unirradiated lesions must not require urgent palliative local treatment.
4. Prior systemic therapy: Patients must be at least 2 weeks from prior chemotherapy, biological agents, immunotherapy or any investigational drug product, with adequate recovery of toxicity,
5. Prior radiation therapy: Patients must be at least 2 weeks from prior radiation therapy
6. Concurrent administration of other cancer specific therapy during the course of this study is not allowed.
7. Only patients 18 years and older are eligible. There is no upper age limit but the patients must be able to medically tolerate the regimen. Adverse event data are currently unavailable on the use immune checkpoint blockade for participants < 18 years of age, and thus children are excluded from this study.
8. ECOG performance status ≤ 1 (see Appendix A).
9. Ability to understand and the willingness to sign a written informed consent document
10. Female subjects of childbearing potential must have a negative serum pregnancy test at screening.
11. Female and male subjects of childbearing potential must agree to use an adequate method of contraception as outlined in section 5.7.1. Contraception is required prior to study entry and for the duration of study participation and 4 months after completion of pembrolizumab administration.
 - Note: Abstinence is acceptable if this is the usual lifestyle and preferred contraception for the subject.
12. Participants must have normal organ and marrow function as defined below:
 - leukocytes $\geq 3,000/\text{mcL}$
 - absolute neutrophil count $\geq 1,500/\text{mcL}$
 - platelets $\geq 100,000/\text{mcL}$

CONFIDENTIAL

This document is confidential. Do not disclose or use except as authorized.

- hemoglobin ≥ 9 g/dl
- total bilirubin $\leq 1.5 \times$ institutional upper limit of normal (ULN)
- AST(SGOT)/ALT(SGPT) $\leq 2.5 \times$ institutional ULN
- AST(SGOT)/ALT(SGPT) For patients with documented liver metastases, $\leq 5 \times$ institutional ULN
- creatinine $\leq 1.5 \times$ within normal institutional ULN

OR

- creatinine clearance ≥ 60 mL/min/1.73 m² for participants with creatinine levels above institutional ULN.
- International normalized ratio (INR) or Prothrombin Time (PT) < 1.5 times the upper limit of normal unless subject is receiving anticoagulant therapy, as long as PT or PTT is within therapeutic range of intended use of anticoagulants.
- Activated Partial Thromboplastin Time (aPTT) < 1.5 times the upper limit of normal unless subject is receiving anticoagulant therapy, as long as PT or PTT is within therapeutic range of intended use of anticoagulants.

Laboratory tests required for eligibility must be completed within 14 days prior study entry. Baseline tumor measurements must be documented from tests within 28 days of study entry. Other non-laboratory tests must be performed within 28 days of study entry.

3.2 Exclusion Criteria

Participants who exhibit any of the following conditions at screening will not be eligible for admission into the study.

1. Metastatic disease impinging on the spinal cord or threatening spinal cord compression.
2. Surgical fixation of bone lesion to be irradiated is required and indicated to provide mechanical stability.
3. Known brain metastases that are untreated, symptomatic, or require therapy to control symptoms. Participants with previously diagnosed brain metastases are eligible if they have completed treatment at least 2 weeks prior to trial therapy initiation, are neurologically stable, and have recovered from the acute effects of radiotherapy or surgery. Any corticosteroid use for brain metastases must have been discontinued without the subsequent appearance of symptoms for ≥ 2 weeks before the initiating protocol therapy. Treatment for brain metastases may include surgery, whole brain radiotherapy, radiosurgery, or a combination as deemed appropriate by the treating physician.
4. Participants who are receiving any other investigational agents.
5. History of allergic reactions attributed to compounds of similar chemical or biologic composition to pembrolizumab or previous toxicity attributed to pembrolizumab or other PD-1 directed therapy that led to permanent drug discontinuation.
6. Uncontrolled intercurrent illness including but not limited to ongoing or active infection, symptomatic congestive heart failure, unstable angina pectoris, cardiac arrhythmia, or psychiatric illness/social situations that would limit compliance with study requirements.
7. Clinically significant electrocardiogram (ECG) abnormality, including a marked Baseline prolonged QT/QTc ([QT interval/corrected QT interval], e.g., a repeated demonstration of a QTc interval > 500 ms).

CONFIDENTIAL

This document is confidential. Do not disclose or use except as authorized.

8. Pregnant women are excluded from this study because immunotherapy has the potential for teratogenic or abortifacient effects. Because there is an unknown but potential risk of adverse events in nursing infants secondary to treatment of the mother with immunotherapy, breastfeeding should be discontinued if the mother is treated on this protocol.
9. Individuals with a history of a different malignancy are ineligible **except** for the following circumstances: if they have been disease-free for at least 2 years and are deemed by the investigator to be at low risk for recurrence of that malignancy; or if diagnosed and treated for cervical cancer in situ, low risk prostate cancer (treated or PSA being monitored without treatment) or basal cell or squamous cell carcinoma of the skin.
10. HIV-positive individuals on combination antiretroviral therapy are ineligible because of the potential for interaction between immunotherapy and these medications.
11. Has history of (non-infectious) pneumonitis that required steroids, evidence of interstitial lung disease or active, non infectious pneumonitis.
12. Active, suspected or prior documented autoimmune disease that has required systemic treatment in the last 2 years with immune modifying agents (e.g. replacement therapy such as thyroxine, insulin or physiologic corticosteroids is not an exclusion criteria).
13. The subject is known to be positive for HepBsAg, or HCV RNA.
14. Lack of availability for follow up assessments.
15. The investigator's belief that the subject is medically unfit to receive pembrolizumab and or unsuitable for any other reason.
16. Has received a live vaccine within 30 days of planned start of study therapy.

3.3 Inclusion of Women, Minorities and Other Underrepresented Populations

Women, minorities and other underrepresented populations are all at risk to develop squamous cell carcinoma of the head and neck, with smoking and alcohol use as the critical risk factors for the disease. Socioeconomically-deprived populations tend to have higher rates of smoking and potentially higher risks of alcohol use, and therefore it is possible this study will be more likely to enroll these individuals. However, there is no reason to think that immune checkpoint blockade combined with radiation will have a differential effect on these populations. The eligibility criteria should not substantially differentially affect their enrollment in the trial, although some minority populations are more likely to have certain comorbid conditions such as heart failure, which may preclude them from the trial.

4. REGISTRATION PROCEDURES

Patients who meet all eligibility criteria (through screening) will be registered in Clinical Trials Management System (CTMS) “OnCore” by the study team. Registration must occur prior to the initiation of protocol therapy. Any participant not registered to the protocol before protocol therapy begins will be considered ineligible.

The investigator will confirm eligibility criteria and a member of the study team will complete the protocol-specific eligibility checklist.

CONFIDENTIAL

This document is confidential. Do not disclose or use except as authorized.

Following registration, participants may begin protocol therapy. Issues that would cause treatment delays should be discussed with the Principal Investigator (PI). If a participant does not receive protocol therapy within 14 days following registration, the participant's registration on the study must be canceled.

The following source documents are required for registering the patient in OnCore:

- Copy of screening lab results
- Signed participant consent form
- Eligibility Checklist

4.1 Registration Process for DF/HCC Institutions

DF/HCC Standard Operating Procedure for Human Subject Research Titled *Subject Protocol Registration* (SOP #: REGIST-101) must be followed.

4.2 General Guidelines for Other Investigative Sites

Eligible participants will be entered on study centrally at the Coordinating Center by the Study Coordinator. All sites should call the Study Coordinator to verify dose level availabilities. Following registration, participants should begin protocol therapy within 10 days. Issues that would cause treatment delays should be discussed with the Sponsor-Investigator. If the subject does not receive protocol therapy following registration, the subject must be taken off study in the CTMS (OnCore) with an appropriate date and reason entered.

4.3 Registration Process for Other Investigative Sites

To register a participant, the following documents should be completed by the participating site and faxed [contact] or e-mailed to the Study Coordinator:

- Copy of hematology panel (CBC with platelets), chemistry panel, coagulation panel (PT/PTT), pregnancy test (if applicable), EKG, TSH, and HIV test results along with any provider's notes that document disease, lesions, or other details relevant to protocol treatment
- Signed participant consent form
- HIPAA authorization form
- Eligibility Checklist

The participating site will then call or e-mail the Study Coordinator to verify eligibility. The Study Coordinator will follow DF/HCC policy (REGIST-101) and register the participant on the protocol. The Study Coordinator will fax or e-mail the participant study number, and if applicable the dose treatment level, to the participating site. The Study Coordinator will also contact the participating site and verbally confirm registration

CONFIDENTIAL

This document is confidential. Do not disclose or use except as authorized.

5. TREATMENT PLAN

[figure not shown]
5.1 Treatment regimen

This is a phase 2 study with one or two cohorts depending on response rate assessing systemic response in patients receiving pembrolizumab in combination with palliative therapy for metastatic SCCHN. Pembrolizumab will be started day 1-10 of radiation, or up to 3 days prior to radiation start, and then administered each 21 day cycle. Radiation in each cohort (A and B) is described in more detail below. Although the toxicities of pembrolizumab and radiation are established, because these two agents are being combined in this protocol each cohort will begin with a 3 to 6 patient safety run in to confirm safety of the combined regimen.

Treatment will be administered on an outpatient basis. Reported adverse events and potential risks are described in section 7. Appropriate dose modifications are described in Section 6. No investigational or commercial agents or therapies other than those described below may be administered with the intent to treat the participant's malignancy during the course of treatment.

The study and treatment schema are shown below:

[figure not shown]
Trial Enrollment – Study Schema

CONFIDENTIAL

This document is confidential. Do not disclose or use except as authorized.

TREATMENT SCHEMA (21 Day Cycles)

CONFIDENTIAL

This document is confidential. Do not disclose or use except as authorized.

Table 1: Pembrolizumab Regimen Description

Agent	Premedication ; Precautions	Dose	Route	Schedule	Cycle Length
Pembrolizumab	Not routinely necessary unless prior infusion reaction.	200 mg, q3w, iv	IV over approximately 30 minutes (range: 20-75minutes). Please refer to Section 8 for compatible infusion set materials including in-line filter.	q3w	21 days (3 week)

Cohort A: Pembrolizumab and hypofractionated radiation

Pembrolizumab will be given within 10 days after starting radiotherapy treatment, or up to 3 days prior to radiotherapy start. Patients in cohort A will receive hypofractionated palliative radiation starting on day 1 to a dose of 8 Gy in each of 3-5 fractions no more frequently than every other day to a single lesion. The specific dose will be determined by the treating radiation oncologist based on clinical indication. Radiation should be completed in the minimum amount of time possible provided radiation is not given on consecutive days, and shall in no instances extend over a period of more than 21 calendar days.

Following this first cycle, pembrolizumab will be continued every 3 weeks. Radiation will, in general, not be repeated during subsequent cycles, except as at the discretion of the Principal Investigator in the case of patients thought to be deriving overall benefit from treatment.

Cohort B: Pembrolizumab and hypofractionated and low dose radiation to multiple lesions

In contrast to Cohort A where a single lesion is irradiated, the goal of cohort B is to irradiate a significant, if not total, volume of visible disease in order to predispose for a systemic immune response. Pembrolizumab will be given within 10 days after starting radiotherapy treatment, or up to 3 days prior to radiotherapy start. Patients in cohort B will receive hypofractionated palliative radiation starting on day 1 to a dose of 8 Gy in each of 3-5 fractions no more frequently than every other day to 1-3 lesions. If the treating radiation believes a dose of 8 Gy is not indicated due to the clinical situation, the dose of radiation may be reduced to 5-6 Gy per fraction. In patients where there are other potential lesions to irradiate, these subjects may also receive palliative radiation to a dose of 20 Gy in 5 fractions to an additional 1-3 lesions, with the goal of treating a significant burden of the patient's measurable disease. Radiation should be completed over a period of approximately 14-21 calendar days, or if more than 3 lesions are irradiated may be partially delivered during the second cycle given logistical radiation planning and treatment constraints. 8

CONFIDENTIAL

This document is confidential. Do not disclose or use except as authorized.

Gy radiation doses will not be given on consecutive days; however, low dose radiation may be administered on subsequent days or on the same days as high dose radiation is administered. In general, a maximum of 2-3 lesions will be treated on any single day, although treating up to 4 lesions is allowed.

Following this first cycle, pembrolizumab will be continued every 3 weeks. Radiation may be administered during subsequent cycles to other lesions using either 5-8 Gy in each of 3-5 fractions or 20 Gy in 5 fractions as deemed appropriate.

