5.4 Agent Administration

5.4.1 Pembrolizumab

Pembrolizumab administration

Sponsor Merck will provide each investigator with adequate supplies of pembrolizumab. Pembrolizumab will be administered by trained medical personnel at the investigational site. Treatment compliance will be monitored through documentation of study treatment administration in the subject's medical record.

Pembrolizumab will be administered in clinic every 21 days (+/- 5 days) during each cycle. It will be administered as a 30 minute IV infusion. Given the variability of infusion pumps from site to site, a window of -10 and +45 minutes is permitted (i.e., infusion time is 30 minutes: -10 min/+45 min).

The Investigator's Brochure contains specific instructions for the preparation of the pembrolizumab infusion fluid and administration of infusion solution.

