5.4.2.6 Timing of radiation treatment

- Cohort A: Three to five treatments of 8 Gy will be delivered no more frequently than every other day and over a period that does not extend over more than 21 days. Pembrolizumab will be given within 10 days after starting radiotherapy treatment, or up to 3 days prior to radiotherapy start.
- Cohort B: Three treatments of 8 Gy will be delivered no more frequently than every other day and over a period that does not extend over more than 21 days. Pembrolizumab will be given within 10 days after starting radiotherapy treatment, or up to 3 days prior to radiotherapy start. 20 Gy in 5 fractions will be delivered to an additional 1-3 lesions that do not require urgent palliation.

5.4.2.7 Organs at risk (OAR) – Treating radiation oncologists will abide by accepted radiation dose constraints, especially in regards to 8 Gy fraction treatment. For patients in Cohort B, a cumulative dose calculation is recommended when irradiated lesions are in close proximity. Guidance for dose constraints are provided in the table 3 below.

Table 3:

Constraints for 3 fraction treatment

Structure	Volume (mL)	Volume Max (Gy)	Max Point Dose (Gy)
Spinal cord	<0.25	18	19.5
Brainstem	<1	18	23
Brachial plexus	<3	22.5	24
Cauda equina	<5	21.9	24
Cochlea			20
Esophagus	<5	21	27
Heart/pericardium	<15	24	30
Trachea and ipsilateral bronchus	<4	15	30
Skin	<10	22.5	24
Stomach	<10	21	24
Duodenum	<5	15	24
Jejunum/ileum	<5	16.2	27

CONFIDENTIAL

This document is confidential. Do not disclose or use except as authorized.

Liver	700mL spared from volume max	17.1	
Kidneys	200mL spared from volume max	14.4	
Lung	1000mL spared from volume max	11.4	
Optic structures	<0.2	15	19.5

Constraints for 5 fraction treatment

Structure	Volume (mL)	Volume Max (Gy)	Max Point Dose (Gy)
Spinal cord	<0.25	22.5	D0.035<30
Brainstem	<0.5	23	30
Brachial plexus	<3	27.5	D0.035<35
Cauda equina	<5	30	35
Cochlea			25
Esophagus	<5	20	35
Heart/pericardium	<15	32	38
Trachea	<4	18	35
Skin	<10	30	D0.035<32
Stomach	<10	18	32
Duodenum	<5	18	32
Jejunum/ileum	<5	20	32
Liver	700mL spared from volume max	21	
Kidneys	200mL spared	17.5	

CONFIDENTIAL

This document is confidential. Do not disclose or use except as authorized.

	from volume max		
Lung	1500mL spared from volume max	13	
Optic structures	<0.2	22	25

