5.5 Definition of Dose-Limiting Toxicity

Pembrolizumab and radiation have been evaluated previously specifically in patients with SCCHN. However, although this is not a phase I protocol, the use of pembrolizumab in combination with high and low dose radiation is relatively novel, and therefore we plan to include a safety-run-in to ensure that treatment is well tolerated in this setting.

Dose-limiting toxicity (DLT) is based on the CTEP Active Version of the NCI Common Terminology Criteria for Adverse Events (CTCAE). DLT refers to toxicities experienced between the start of treatment and cycle 3, day 1 of pembrolizumab (the DLT evaluation period). A DLT will be defined as follows:

DLTs will be graded according to the National Cancer Institute's CTCAE v4.0 (<http://ctep.cancer.gov/forms/CTCAEv4.pdf>). A DLT is any event that: a) occurs during the DLT evaluation period; and b) is possibly, probably, or definitely related to the administration of pembrolizumab and radiation; and c) fulfills any of the following criteria:

1. Any Grade ≥ 3 pneumonitis, neurological event or uveitis.
2. Any Grade 2 pneumonitis, neurological event or uveitis, with the *following exception*:
 - Grade 2 pneumonitis, neurological event or uveitis that downgrade to Grade ≤ 1 within 3 days after onset, whereby maximal supportive care, including systemic corticosteroids, is permitted.
3. Any *other* Grade ≥ 3 toxicity, with the *following exceptions*:
 - Grade 3 irAEs that downgrade to Grade ≤ 2 within 3 days, or to Grade ≤ 1 or baseline within 14 days after onset, whereby maximal supportive care, including systemic corticosteroids, is permitted.
 - Grade 3 colitis that downgrades to Grade ≤ 2 within 7 days after onset, whereby maximal supportive care, including systemic corticosteroids, is permitted.

CONFIDENTIAL

This document is confidential. Do not disclose or use except as authorized.

- Grade 3 asymptomatic endocrinopathy, managed with or without systemic corticosteroid therapy and/or hormone replacement therapy.
- Grade 3 inflammatory reaction attributed to a local antitumor response (e.g., inflammatory reaction at sites of metastatic disease, lymph nodes, etc.).
- Grade 3 fatigue for \leq 7 days.
- Grade 3 infusion-related reaction (first occurrence and in the absence of steroid prophylaxis) that resolves within 6 hours with appropriate clinical management.

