13. STATISTICAL CONSIDERATIONS

13.1 Study Design/Endpoints

This phase 2 study will enroll patients who have previously progressed on PD-1 directed therapy, for whom response to pembrolizumab monotherapy is unlikely. These patients usually progress rapidly within a span of a few months and the expected progression-free survival rate at 3 months is about 35%. Therefore, the combined treatment will be considered promising and worthy of further evaluation if there is evidence that the 3-month progression-free survival (PFS) is approximately 65%. A two-stage design will be employed and a safety run-in phase will be conducted using a 3+3 design.

Safety Run-In:

The safety run-in phase will follow a 3+3 design. Initially 3 patients will be entered. If none of the 3 patients experiences dose-limiting toxicity (DLT), the safety run-in phase will end and the study will proceed. If 1 out of 3 patients experiences a DLT, an additional 3 patients will be entered. If none of the additional 3 patients experiences a DLT, the study will proceed. If at any time 2 (or more) patients experience a DLT in the run-in phase, the study will be terminated. Treatment safety will continue to be monitored after the run-in phase. If there are 33% or more of patients with a DLT at any time during the phase II portion, the study will pause and a detailed safety analysis will be conducted.

Phase II:

A two-stage design will be used in the phase II portion of this study. The first stage will accrue 6 patients and the patients in the run-in phase will be included in the stage I accrual. If at least 2 patients are progression-free and alive at 3 months, an additional 13 patients will be entered. If 10 or more patients are progression-free and alive at 3 months among 19 patients, the combination treatment will be considered worthy of further study for this group of patients. With this design, we will have 90% power to test the PFS rate of 65% vs. 35% based on a 0.08 level one-sided test.

If only 0 or 1 patient is progression-free at 3 months among the 6 patients in stage I accrual, the same design (safety run-in plus two-stage design) will be used to examine the combination treatment of pembrolizumab plus hypofractionated and low dose radiation (cohort B).

CONFIDENTIAL

This document is confidential. Do not disclose or use except as authorized.

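### The DLT window closes at pembrolizumab cycle 3 day 1, yet part of the Cohort B radiation may be given in cycle 2, so late deferred fractions can have as little as 1 day of observation under the run-in rule

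*Combined protocol and SAP*

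**What the plan says.** **DLT window.** Section 5.5 gives one definition for both cohorts: "DLT refers to toxicities experienced between the start of treatment and cycle 3, day 1 of pembrolizumab (the DLT evaluation period"). Falling inside that period is one of the conditions for an event to be a DLT. The window is tied to the pembrolizumab cycle and not to the last radiation fraction.

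**Radiation timing in 5.1.** For Cohort A, radiation "shall in no instances extend over a period of more than 21 calendar days". For Cohort B the text is looser: "Radiation should be completed over a period of approximately 14-21 calendar days", with the exception that it "if more than 3 lesions are irradiated may be partially delivered during the second cycle given logistical radiation planning and treatment constraints". No latest day in cycle 2 is stated. Section 5.1 also allows Cohort B radiation to other lesions in later cycles.

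**Run-in rule in 13.1.** "If none of the 3 patients experiences dose-limiting toxicity (DLT), the safety run-in phase will end and the study will proceed". With 1 DLT in 3, three more patients enter and the study proceeds if none of them has a DLT; with 2 or more DLTs it is terminated. Cohort B uses the same design. After the run-in, the study pauses if 33% or more of patients have a DLT. No minimum observation after radiation is required.

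**Other timing statements.** Section 5.4.2.6 has the Cohort B 8 Gy treatments given "over a period that does not extend over more than 21 days", but sets no limit for the 20 Gy in 5 fractions. The study calendar marks radiotherapy only in C1 D1-D21; its footnote b accepts radiotherapy in later cycles with the PI's permission. Section 5.3.1 places the research blood draw of about week 4 after all radiation is finished.

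**The concern.** Section 5.1 says that each cohort starts with a run-in to confirm that the combination is safe. The goal of Cohort B is to irradiate much or all of the visible disease, so patients with more than 3 treated lesions are central to what its run-in should test. They are also the only patients whose initial course may run into cycle 2, where the fixed end of the window cuts observation short.

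An event of DLT severity that follows a deferred fraction but appears after cycle 3 day 1 is not a DLT by definition. It cannot trigger the three extra patients, it cannot terminate the study, and it does not count toward the 33% pause rule, which counts the same DLTs. At stake is whether a Cohort B regimen with too much toxicity is cleared more often than the 3+3 rule implies.

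**Working it through.** The plan states no figure for this point, so there is none to reproduce. The check is a day count followed by the exact pass probability of the 3+3 rule.

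**Step 1. Inputs.**
- Pembrolizumab start relative to radiation start (5.1): "Pembrolizumab will be given within 10 days after starting radiotherapy treatment, or up to 3 days prior to radiotherapy start". So s runs from -3 to +10 days, with radiation starting at day 0.
- Cycle length (5.4.1): "Pembrolizumab will be administered in clinic every 21 days (+/- 5 days) during each cycle".
- End of window (5.5): cycle 3 day 1, which falls at day s + 42 with nominal cycles.

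**Step 2. Course finished on its day 21 (day 20 counting from 0).** Observation = (s + 42) - 20 = s + 22.
- s = -3: 19 days. s = 0: 22 days. s = +10: 32 days.
- If both pembrolizumab intervals are 5 days short, subtract 10: 9, 12 and 22 days.

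**Step 3. Fractions deferred to cycle 2 (nominal cycles).** Cycle 2 day 1 is day s + 21, and s cancels.
- Last fraction on cycle 2 day 1: (s + 42) - (s + 21) = 21 days.
- Last fraction on cycle 2 day 21: (s + 42) - (s + 41) = 1 day.
- Five consecutive daily fractions from cycle 2 day 1 end on day s + 25 and leave 17 days.

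**Step 4. Effect on the run-in.** Let p be the true DLT rate, m the share of DLTs falling after the window, averaged over all run-in patients, and q = p(1 - m) the rate that the rule can see. Then

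P(proceed) = (1 - q)^3 + 3q(1 - q)^2 × (1 - q)^3 = (1 - q)^3 + 3q(1 - q)^5.

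The documents give neither p nor m; both are assumptions here.

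| True rate p | Share missed m | Visible rate q | P(proceed) |
|---|---|---|---|
| 0.30 | 0 | 0.30 | 0.343 + 0.151 = 0.49 |
| 0.30 | 1/6 | 0.25 | 0.422 + 0.178 = 0.60 |
| 0.30 | 1/2 | 0.15 | 0.614 + 0.200 = 0.81 |
| 0.40 | 0 | 0.40 | 0.31 |
| 0.40 | 1/2 | 0.20 | 0.71 |

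The one-sixth row corresponds, for example, to one third of patients affected, each losing half of their DLTs (1/3 × 1/2 = 1/6). The one-half rows need every run-in patient to be affected and to lose half.

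**The case against.** The strongest case for the plan has four parts.

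1. **The gap is partial.** Only part of the radiation may move to cycle 2, and only with more than 3 treated lesions. Cycle 1 radiation and the first pembrolizumab doses stay under observation. A run-in of 3 to 6 patients may include nobody affected. This stands, and it is why the one-half rows are upper illustrations.
2. **Other sections point to earlier completion.** Section 5.4.2.6, the calendar and 5.3.1 all do. If the 21-day limit in 5.4.2.6 governs, the deferred part is mainly the 20 Gy courses, and section 2.3 describes lower-dose palliative radiation as very well tolerated. This narrows the concern but does not remove it: 5.1 gives explicit permission, does not restrict which part may be deferred, and is not reconciled with the other sections.
3. **Late events are not lost.** Adverse events are collected to 30 days after the last intervention (section 6), safety monitoring continues after the run-in (13.1), and the DSMC reviews toxicity (12.2). This also stands, but none of it feeds a late event into the 3+3 or 33% rules. The discretion in 5.5 to reclassify events covers lower-grade events, exempt events and patients who are not evaluable; it does not lengthen the window.
4. **Exposure is limited.** Run-in patients count toward the 6 in stage I, so a run-in wrongly cleared after 3 patients adds at most 3 before the stage I decision. That is correct, but the decision is on 3-month PFS, so an active regimen with excess toxicity could still go on to the further 13 patients.

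A reader might infer more than the documents support. They do not show that affected patients have almost no observation after radiation: 1 day is the extreme of a 1 to 21 day range and applies to the deferred fractions only. They do not say that the window was designed around a 21-day course. Nor do they guarantee Cohort A about 21 days: step 2 gives 19 to 32 days nominally and 9 to 22 with short intervals.

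**Conclusion.** The point holds as a statement of what the plan permits. For Cohort B patients with more than 3 treated lesions, toxicity from fractions deferred late into cycle 2 can fall outside both safety rules.

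The size is uncertain. At an assumed true DLT rate of 30%, the pass probability moves from 0.49 to 0.60 if one sixth of DLTs are missed, and to 0.81 only if half are missed with every run-in patient affected. The last figure is not an expected value. The figures rest on the assumed DLT rate, the assumed share missed, and independence between patients; the day counts rest on nominal 21-day cycles except where stated. The change is worth making because it closes a gap in a formal safety decision at small cost.

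**What to change.** - **Section 5.5.** End the Cohort B DLT window at the later of cycle 3 day 1 and a fixed interval after the last fraction of the initial radiation course. The sponsor should set and justify the interval; step 2 gives the nominal 19 to 32 days as a reference, not as a protocol minimum.
- **Section 13.1.** State that the 3+3 rule and the 33% pause rule for Cohort B use that window.
- **Reconcile** 5.1 with 5.4.2.6 (a 21-day limit on the 8 Gy part, none stated for 20 Gy in 5 fractions), the study calendar (radiotherapy in C1 D1-D21) and 5.3.1 (week 4 draw after all radiation).

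No dose or radiation schedule is proposed.

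**Cost.** A few sentences of text, and a longer Cohort B run-in for affected patients only. The added time is the chosen interval less the days already observed by cycle 3 day 1. With an interval of 21 days, taken for illustration, and a last fraction on cycle 2 day 21, that is 21 - 1 = 20 days, or about 3 weeks; a longer interval would add correspondingly more.
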